B) At 2 years, patients with asymptomatic carotid stenosis who develop cognitive impairment will differ in these characteristics compared with similar patients that remain unchanged. The differential mean value for plaque area, volume, composition, microembolic counts, serum pro-inflammatory marker levels and cerebrovascular reactivity will be tested between the two groups using t-tests. The detectable difference for each of these factors is again very conservatively estimated to be the same differences of 0.4 SD with 90% power, and 0.3 SD with 80% power (now the SD of each of these factors). Such a small change relative to the SD of each of these factors is reasonable to define as being small enough to detect all “clinically important changes.”

Specific Aim 3 is designed to explore whether cognitive changes in patients with asymptomatic carotid stenosis correlate with changes in health-related quality of life. We hypothesize that at 2 years, regardless of plaque features, cognitive change will correlate with change in health-related quality of life measures.

For this aim, the principal outcome variables will be the change in quality of life measures (Frenchay and SF-36) between baseline and follow-up. The outcome event will be cognitive change score at the corresponding follow-up time point. Initially, the correlation between each quality of life change score and corresponding cognitive change score will be explored in a univariate fashion using t-tests. Subsequently, multivariate analysis will be used to determine the independent impact of altered cognition on quality of life after controlling for additional patient variables such as age, gender, mood, medical co-morbidities, and degree of stenosis. Independent predictors of change in quality of life will be selected based on $p \leq 0.05$. With the sample size of 142, a correlation of 0.2 between change in cognitive function and change in quality of life can be detected with 90% power, and a correlation of 0.18 can be detected with 80% power.

Potential difficulties and Alternate approaches/analyses:

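### Aim 3 names t-tests for a correlation of two continuous change scores and selects predictors at p ≤ 0.05; both rules need replacing, though the harm depends on how they are read

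*Combined protocol and SAP*

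**What the plan says.** Under Sample Size and Data Analysis, item 2, Specific Aim 3 takes change in SF-36 and Frenchay as the principal outcomes. It then also gives cognition an outcome role: "The outcome event will be cognitive change score at the corresponding follow-up time point". There are two steps.

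- **Univariate step:** "the correlation between each quality of life change score and corresponding cognitive change score will be explored in a univariate fashion using t-tests". No coefficient, grouping or cut-point is given.
- **Multivariable step:** the independent impact of altered cognition is to be determined after "controlling for additional patient variables such as age, gender, mood, medical co-morbidities, and degree of stenosis". The plan adds: "Independent predictors of change in quality of life will be selected based on" p ≤ 0.05. It does not say whether any term is forced into the model.

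The power statement is for a correlation in 142 patients. It claims 90% power at r = 0.2 and, for the lower power level, says that "a correlation of 0.18 can be detected with 80% power".

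**The concern.** A t-test in its everyday sense compares two group means. Just above Aim 3, that is how the plan uses the term for Aim 2B, where mean values "will be tested between the two groups using t-tests". Carried over to Aim 3, it would mean splitting patients on cognitive change. That discards information and no longer matches a power statement written for a correlation.

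The selection rule conflicts with the stated purpose. Estimating the adjusted effect of one prespecified exposure requires that exposure and its confounders to stay in the model. If terms stay only when p ≤ 0.05, a real confounder that misses the threshold is removed and part of its effect moves into the cognition slope. Cognition itself may be dropped, or reported only when significant. Intervals calculated after such selection are too narrow.

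If the wording stays open, the cut-point and the retained covariates could be chosen after the data are seen.

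**Working it through.** **Inputs.** n = 142 and the pairs (r = 0.20, 90%) and (r = 0.18, 80%) come from the Aim 3 text. The stenosis group is the right base, because Study Procedures, item 1, lists only cognitive assessments for controls at follow-up. Alpha is not stated for the power figures; two-sided 0.05 is assumed. All 142 patients are taken as complete.

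**1. The plan's own power figures (continuous test).** Fisher z: power = Φ(atanh(r)·√(n−3) − 1.960), with √139 = 11.790.

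- r = 0.20: 0.2027 × 11.790 − 1.960 = 0.430, power 66.7% (stated 90%).
- r = 0.18: 0.1820 × 11.790 − 1.960 = 0.186, power 57.4% (stated 80%).
- Detectable r at 90%: tanh((1.960 + 1.282)/11.790) = 0.268. At 80%: tanh((1.960 + 0.842)/11.790) = 0.233.
- n needed: about 259 for r = 0.20 at 90%, and about 240 for r = 0.18 at 80%.

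A noncentral t gives 67.6% and 58.1%. One-sided 0.05 gives detectable r of 0.243/0.208, and one-sided 0.10 gives 0.214/0.178. With n = 284, two-sided power is 92.5%/86.2%. No variant reproduces both stated figures.

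**2. If the t-test compares groups.** Splitting a normal variable at quantile q multiplies r by φ(z_q)/√(q(1−q)). At the median this is 0.3989/0.5 = 0.798, and 0.798² = 0.637, so the split is worth about 90 of the 142 patients.

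| True r | Continuous test | Median split | 34/66 split |
|---|---|---|---|
| 0.18 | 57.4% | 39.9% | 37.9% |
| 0.20 | 66.7% | 47.5% | 45.2% |

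Simulation (20,000 runs) gives 57.8% against 39.8%, and 67.3% against 48.5%, for the continuous test and the median split. The 34/66 split is illustrative only. The 34% is the share with cognitive decline in a 32-patient subset cited in the background, not a cut-point set for Aim 3.

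**3. If the t-test is of a coefficient.** The usual test of a correlation or a simple regression slope is a t-test on n − 2 degrees of freedom. Power is then the continuous column above and nothing is lost.

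**4. If p ≤ 0.05 decides what stays.** The documents give no confounder correlations, so every structure here is an assumption. Backward elimination at n = 142 with no true cognition effect retained cognition as follows:

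| Assumed confounders | False positives |
|---|---|
| One (correlation 0.2 with cognition, slope 0.15) plus four noise covariates | 5.6% |
| Six at correlation 0.1, alternating signs | about 6% |
| Six at correlation 0.1, same direction | about 7% |
| One (correlation 0.4, slope 0.2) plus four noise covariates | 7.4% |
| Six at correlation 0.3, same direction | 17–21% |

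The full model stayed near 5% (4.1–6.0%). The last row is near a worst case: six independent covariates at 0.3 explain 6 × 0.09 = 54% of the variance in cognition.

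With a true slope of 0.20 and the fourth structure, the slope averaged 0.268 in the runs that retained cognition, and 95% CI coverage was 89.6%. The full model gave 0.198 and 95.1%. Part of that excess comes from keeping only significant results. Without any confounder, reporting a correlation only when p ≤ 0.05 turns a true 0.20 into a mean of 0.244, and 0.18 into 0.234.

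**The case against.** The strongest reply is that neither harm is written into the plan. The sentence speaks of testing a correlation, power is given for a correlation, and Aim 3 defines no groups. Where the plan compares groups, in Aim 2B, it says so. For Aim 2A it states that variables will be analysed as continuous because that is more powerful. Similarly, no stepwise procedure is named. The p ≤ 0.05 sentence also fits a significance threshold inside a model that already adjusts for the listed covariates, and dropping cognition would sit badly with that model's purpose.

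This stands to the extent that a reader might infer that Aim 3 will certainly dichotomise cognition and certainly run backward elimination. The documents do not establish either, so the losses in steps 2 and 4 are conditional. It is also right that the higher false-positive figures need strong assumed confounding, and that the shortfall from the stated power is present before any split.

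It does not remove the point. The group reading remains plausible: Aim 2B uses the term that way nearby, the objectives phrase Aim 3 in terms of cognitive impairment, and the additional follow-up asks for correlation analyses by name. Selecting predictors is the usual language of variable selection, the covariate list is open-ended, and nothing protects the cognition term.

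**Conclusion.** The point holds in conditional form. The Aim 3 rules as written do not fit an aim that concerns the adjusted association of two continuous scores. If they are applied as group t-tests, a median split costs about 17 to 19 points of power at the plan's own correlations. If p ≤ 0.05 governs retention, the cognition effect can be biased, with false positives at about 6–8% under mild assumed confounding and 17–21% near the worst case, against 5% for a fixed model. Under the benign readings neither harm occurs.

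Separately, and whichever reading applies, the stated power is too high at two-sided 0.05 by about 23 points in each case (90 − 66.7 and 80 − 57.4).

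Severity is modest. Aim 3 is described as exploratory and the primary hypothesis belongs to Aim 1. It is still a specific aim with its own hypothesis and power claim, and the same edit serves under every reading.

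**What to change.** In Sample Size and Data Analysis, item 2, Specific Aim 3:

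1. Replace the t-tests with a Pearson or Spearman correlation (state which) and its 95% CI, on the continuous change scores.
2. Replace selection at p ≤ 0.05 with one linear regression per quality-of-life score: change in that score on cognitive change, always keeping cognitive change and a closed covariate list (age, gender, mood, degree of stenosis and a defined co-morbidity measure). State that quality-of-life change is the outcome and cognitive change the exposure.
3. Report the cognition slope with its CI whatever its p-value.
4. Restate the power: at n = 142 and two-sided 0.05, about r = 0.27 at 90% and r = 0.23 at 80%; or about 67% and 57% power at r = 0.20 and 0.18. The new analysis does not restore the stated figures.

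The cost is wording, plus a decision on how co-morbidity is measured. No new visits are needed. With cognition and five covariates entered as single terms, 142 − 7 = 135 residual degrees of freedom remain. The downside is slightly wider intervals when a covariate turns out to be irrelevant.

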Tromso study	7/7/2010 11:41 AM	7/7/2010 11:41 AM
CREST REVIEW	7/7/2010 11:41 AM	7/7/2010 11:41 AM
Endarectomy for symptomatic carotid artery stenosis	7/7/2010 11:40 AM	7/7/2010 11:40 AM

3 * Provide a list of 3 keywords or search terms (1 per line) relevant to your research that would help potential participants find your study using search engines:

Keyword 1: Carotid

Keyword 2: Cognition

Keyword 3: Plaque

ID: VIEW4E02805A7E400
Name: v2_Supporting Literature

View: v2_Study Procedures

Study Procedures

If you uploaded a separate research protocol document in the 'Research Protocol' page, cite the applicable section and page numbers from that document in the answer boxes below. (If this study is a collaborative UM/VA study please list each procedure that is being conducted and the locations where it is being conducted.)

1 * Describe all procedures being performed for research purposes only (these procedures would not be done if individuals were not in the study) and when they are performed, including procedures being performed to monitor subjects for safety or to minimize risks:

The schedule for major evaluation components is provided in Table II of the protocol page 32

The time required to obtain the information is provided in Table III of the protocol page 32.

To assess the stated endpoints, our study will establish for each patient, the baseline demographics, vascular risk factor profile, neurologic status (history, neurologic examination, NIHSS), cognitive function (cognitive function tests), plaque information (3D B-mode imaging), microembolic counts (TCD testing), inflammatory status (serum pro-inflammatory markers), perfusion status (cerebrovascular reactivity) and quality of life (SF36, Frenchay index). To assess change in status we will measure for each patient,

follow-up cognitive function, plaque information, microembolic counts, inflammatory status, perfusion status, and quality of life, at 1 and 2 years post-recruitment. The stenosis-free control subjects will undergo an ultrasound carotid assessment at baseline (to rule out stenosis), and assessments of cognitive function at baseline and at 1 and 2 years post-recruitment.

**With regards to the planned additional follow-up, participants will attend one session of approximately 2 hours duration.

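### Aim 3 power is overstated: with 142 patients, correlations of 0.20 and 0.18 have about 67% and 57% power, not 90% and 80%

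*Combined protocol and SAP*

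**What the plan says.** The statement is in Sample Size and Data Analysis, item 2, at the end of the Specific Aim 3 text. Its first part, for which 90% power is claimed, reads: "With the sample size of 142, a correlation of 0.2 between change in cognitive function and change in quality of life can be detected". Its second part reads: "a correlation of 0.18 can be detected with 80% power".

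The same text sets out what is tested and in whom. The aim is to "explore whether cognitive changes in patients with asymptomatic carotid stenosis correlate with changes in health-related quality of life", so the population is the stenosis group, planned at 142. The hypothesis in this section is that "cognitive change will correlate with change in health-related quality of life measures". The only significance level given for the aim is p ≤ 0.05, as the rule for choosing independent predictors in the multivariable model. The power sentence itself gives neither alpha nor sidedness.

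Study Procedures, item 1, schedules quality of life for patients at baseline, 1 year and 2 years. For controls it says: "The stenosis-free control subjects will undergo an ultrasound carotid assessment at baseline (to rule out stenosis), and assessments of cognitive function". It lists no quality-of-life assessment for them.

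**The concern.** A correlation of 0.20 is small, and 142 pairs is a modest number for detecting it with 90% power. The sample size, correlation and power are all in one sentence, so the claim can be checked directly.

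Aim 3 asks whether cognitive change matters to patients' quality of life. If the stated powers were right, a non-significant result would be fairly strong evidence against a correlation of about 0.2. If they are too high, a reader who relies on them will take a null result as more informative than it is.

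**Working it through.** **Inputs**

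- n = 142, r = 0.20 with 90% power, r = 0.18 with 80% power: Sample Size and Data Analysis, item 2, Specific Aim 3.
- Alpha = 0.05, two-sided: an assumption. It takes the p ≤ 0.05 used elsewhere in this aim and the non-directional hypothesis in this section. One-sided 5% is shown as well.

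**Formula.** Fisher z test of zero correlation: power = Φ(atanh(r)·√(n−3) − z), with z = 1.960 (two-sided 5%) or 1.645 (one-sided 5%). The opposite tail is negligible here. For n = 142, √139 = 11.790.

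**Power at the plan's correlations, n = 142, two-sided 5%**

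- r = 0.20: atanh = 0.2027; 0.2027 × 11.790 = 2.390; 2.390 − 1.960 = 0.430; Φ = 66.6%. The plan says 90%.
- r = 0.18: atanh = 0.1820; 0.1820 × 11.790 = 2.146; 2.146 − 1.960 = 0.186; Φ = 57.4%. The plan says 80%.

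A noncentral t calculation gives 67.6% and 58.2%. Simulating 100,000 bivariate-normal samples of 142 gives 67.2% and 57.6%.

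**Correlation detectable with 142**

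- 90% power: tanh((1.960 + 1.282)/11.790) = tanh(0.2749) = 0.268.
- 80% power: tanh((1.960 + 0.842)/11.790) = tanh(0.2376) = 0.233.

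**Sample size the plan's pairs would need**

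- r = 0.20, 90%: (3.242/0.2027)² + 3 ≈ 259.
- r = 0.18, 80%: (2.802/0.1820)² + 3 ≈ 240.

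**Attempts to reproduce the plan's figures**

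| Setting | Power at r = 0.20 | Power at r = 0.18 |
|---|---|---|
| Plan | 90% | 80% |
| n = 142, two-sided 5% | 66.6% | 57.4% |
| n = 142, one-sided 5% | 77.2% | 69.2% |
| n = 142, one-sided 10% | 86.6% | 80.6% |
| n = 284, two-sided 5% | 92.5% | 86.2% |
| 0.20 and 0.18 read as R², n = 142, two-sided 5% | over 99.9% | over 99.9% |

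No setting gives both figures. One-sided 10% matches only the second, at a level the documents never mention. At n = 142 the plan's powers would need a two-sided alpha of about 0.27 for the first pair and 0.19 for the second.

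**Attrition.** Stroke at the upper expected rate of 2% per year for 2 years leaves 142 × 0.96 ≈ 136 patients. Power is then 64.7% and 55.5%.

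**What a null result could exclude.** With 142 patients the 95% interval on the z scale is ±1.960/11.790 = ±0.166. As an illustration, an observed r of 0.10 is not significant, and its interval runs from tanh(0.100 − 0.166) = −0.07 to tanh(0.100 + 0.166) = 0.26. A correlation of 0.20 lies well inside it.

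**The case against.** Five points can be made for the plan.

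1. **Alpha and sidedness are not stated for this sentence.** That is correct, and the figures of 67% and 57% depend on two-sided 5%. Specific Aim 3 as worded under Justification, Objective, & Research Design is directional (impairment going with a reduction in quality of life), so a one-sided test could be argued. It still gives only 77% and 69%. The condition should be stated, but it does not rescue the claim.

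2. **The figures might have been meant for all 284 subjects.** With 284, power is 92.5% and 86.2%, and the detectable correlations are 0.19 and 0.17. That is closer but not a match, and the documents do not show how the figures were obtained. Whether controls complete the questionnaires is not fully settled: the Study Procedures narrative lists none for them, but the schedule table it refers to is not in the text available. The point does not depend on this, because the sentence itself says 142 and the aim is confined to stenosis patients.

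3. **The aim is exploratory, and the true association may be stronger.** The plan does speak of exploring, and its preliminary data pair a composite cognitive change of 0.41–0.7 with a quality-of-life change above 2 SD. If the true correlation is about 0.27 or more, 142 patients do give 90% power. That is a reason to state 0.27; it does not make the figure for 0.20 correct. It is also fair that no passage commits the investigators to reading a null Aim 3 result as excluding 0.2. The risk lies in how a reader would use the stated power.

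4. **Attrition is said to be already accounted for.** The plan says this of stroke losses, yet the Aim 3 sentence uses the full 142. The effect of stroke alone is only about 2 points.

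5. **Recruitment is closed** (VA-Specific Criteria), so a corrected planning figure changes neither enrolment nor conduct. This is true, and the value of the correction lies in interpretation.

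**Conclusion.** The statement is wrong as written. With 142 patients and a two-sided 5% test, power is about 67% at a correlation of 0.20 and 57% at 0.18, about 23 points below each stated figure. The chance of missing a true correlation of that size is about 33% and 43%, against the 10% and 20% implied. Under one-sided 5% it is 23% and 31%, still well above. No other passage corrects the sentence.

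The exact sizes rest on the assumed two-sided 5% level, approximately bivariate-normal change scores, and all 142 patients contributing both measures; losses would lower power further. The error affects a secondary aim, so it should be corrected, but it leaves the Aim 1 comparison and its sample size untouched.

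**What to change.** Replace the Aim 3 power sentence with: *With 142 patients, a correlation of 0.27 can be detected with 90% power and 0.23 with 80% power (two-sided 5%); power is 67% for a correlation of 0.20 and 57% for 0.18.* If fewer patients have both change scores, restate the figures for that number.

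Add that each correlation between cognitive change and quality-of-life change will be reported with its 95% confidence interval, so that a non-significant result is not read as no relationship.

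The cost is a one-sentence replacement and a reporting line. The stated power becomes less favourable. No extra patients, visits or measurements are needed.

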Specific Aim 1 will assess if patients with asymptomatic carotid stenosis differ in cognitive function compared to age-matched controls without carotid stenosis but with similar vascular risk profiles. We hypothesize that in patients with asymptomatic carotid stenosis $\geq 50\%$ who survive stroke free for 2 years; the change in overall and domain-specific cognitive function will be significantly different compared to those without stenosis. The study will recruit 284 subjects and will detect a clinically significant difference in cognitive score with 90% power. We will use a novel battery of cognitive tests specifically developed to address the unique issues relating to carotid stenosis.

Specific Aim 2 will define plaque-morphometric, biologic, and hemodynamic characteristics that correlate with cognitive impairment in patients with asymptomatic carotid stenosis. We hypothesize that carotid plaque architecture, plaque composition, microembolic counts, serum pro-inflammatory markers, and cerebral hypoperfusion could each mediate cognitive decline over a 2-year follow-up period. We will implement a novel clinical 3D B-mode ultrasound imaging technique developed to obtain reliable serial plaque measurements.

Specific Aim 3 will measure the impact of cognitive impairment on quality of life. We hypothesize that at 2 years, regardless of plaque features, cognitive impairment will correlate with a reduction in health-related quality of life measures.

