3 * Describe the duration of an individual participant's participation in the study:

Duration of participation for subjects will be for 2 years following enrollment.

Due to enrollment still ongoing, participation will extend for another two visits after their 2 year follow-ups have been completed for already enrolled patients. Until all follow-up for all enrolled patients is complete, we will continue to see patients on a yearly basis and administer cognitive functioning battery. Also, for patients who have already completed their follow-up, we will ask if they are agreeable to also submitting a blood sample for genetic testing and obtain that if they are willing to continue to be followed.

**With regards to the planned additional follow-up, subjects will be invited to participate in one additional follow-up visit that will be approximately two hours in duration.

4 * Describe the duration of the entire study:

Study timeline

Overall, the project will require approximately 4 years to complete; separated into four major activities. The first year will be devoted to planning, IRB application, and commencing data acquisition. We anticipate an early start to data collection since our center has an established recruitment and treatment infrastructure in place. The projected duration of patient recruitment is 2 years. Follow-up will begin immediately after recruitment, and those patients who entered as late as month 24 will be followed until conclusion of the trial.

**With regards to the planned additional follow-up, the entire duration of the study will be one year.

5 * Describe any additional participant requirements:

Original ACCOF protocol: Quality of life questionnaires will have to be completed by the participant.

**With regards to the planned additional follow-up, there will be no additional participant requirements other than those listed above in question 1.

ID: VIEW4E0280585B400
Name: v2_Study Procedures

View: v2_Sample Size and Data Analysis

Sample Size and Data Analysis

If you uploaded a separate research protocol document in the 'Research Protocol' page, cite the applicable section and page numbers from that document in the answer boxes below.

1 * Provide the rationale and sample size calculations for the proposed target population:

Statistical Analysis

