Practice effect on cognitive testing. Since patients will be exposed to the same cognitive tests at different periods, scores may improve due to the “practice effect.” In this study, the practice effect is anticipated to be low since tests are being repeated at 1 year intervals (baseline, 1 year, and 2 years post-recruitment). Alternate test forms will be used wherever possible. Reliable change analyses will be used to determine if changes detected in the composite score, as well as on specific domain scores of interest exceed that which is expected based on repeated exposure to the measure, error variance, and maturation.

Additional analysis of Aim 1 including patients with post-recruitment stroke. Based on prior randomized trials, it is anticipated that approximately 1-2% of our patients per year will suffer a stroke2. Separating primary cognitive deficits from poor performance on cognitive testing due to disability associated with stroke is difficult. Furthermore, patients that develop stroke during follow-up will require carotid revascularization with elimination of the stenosis per standard of care. That is why the proposed study will exclude such patients when evaluating cognitive outcome. This attrition has been accounted for in the power analysis, and will not affect our results. Moreover, for those unable to complete testing due to stroke, the statistical E-M algorithm (Laird and Ware106) will be used to provide an estimate of the mean score in the presence of the missing data. This statistical approach has been shown to produce unbiased estimates that are more precise than alternative approaches in the presence of data that are missing.

Additional analysis of Aim 1 comparing baseline cognition in the two groups. We feel that a major strength of the application is the longitudinal data collection and comparisons of change scores. This is statistically much more powerful than a simple cross-sectional comparison. However, we will have data on baseline cognitive scores for patients versus control subjects. In an additional analysis we will perform a simple comparison of these scores to measure differences at baseline in the two populations.

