Additional analysis of Aim 2 focusing on correlations with stroke during follow-up. For the patients in the cohort that suffer a stroke during follow-up, we will have plaque architecture, plaque composition, microembolic count, pro-inflammatory marker, and perfusion information, prior to their stroke. We are aware of the fact that the focus of our study is not on stroke; furthermore, these 5 to 10 patients will be too few to derive statistically strong conclusions. However, we will analyze available data and report additional conclusions on plaque correlates of stroke, if the information is hypothesis-generating.

TCD microembolic counts. We are aware that automated emboli counts and classifications are subject to the effectiveness of signal filtering algorithms. Therefore filters will be programmed according to criteria validated in consensus documents70. As an added precaution, we will analyze all spectral recordings manually to confirm embolic counts.

Temporal consistency. We are aware that the significance of outcomes and interpretation of mechanisms may be influenced by differential temporal effects. While the primary statistical approach will be to evaluate change scores over 2 years; we will describe the temporal pattern of cognitive changes and assess if the hypotheses are temporally consistent at the 1-year time interval.

Vascular risk factor distribution. We realize that the control group will include patients with a heterogeneous mix of one or more vascular risk factors. It is likely that one risk factor may have a larger influence on cognitive function than another; or multiple risk factors together in a patient may influence cognition more than in a patient with one risk factor. However, in a study of this size with finite resources, it will not be possible to expand the control group to the large numbers required to study the effects of each risk factor alone and in various combinations. In any case, that is well beyond the focus of this investigation. We will closely monitor the control subjects to ensure no unusual heterogeneity of cognitive scores. If such is found, we will then focus on recruiting patients with limited (one or two) risk factors alone.

**With regards to the planned additional follow-up, we will perform standard correlation analyses between cognitive scores of the subjects obtained previously with physical function scores that we plan to obtain during the additional follow-up.

ID: VIEW4E02806052800

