** With regards to the planned additional follow-up, all subjects enrolled in ACCOF will be contacted directly to gauge their interest in participating. There is no script being used to recruit these subjects other than information contained in the informed consent.

2 * Describe measures that will be implemented to avoid participant coercion or undue influence (if not applicable to the study,

enter "N/A"):

The study purpose, procedures, risks and benefits will be explained to the patient. An evaluation to sign consent form will be used to determine the mental eligibility of the consenting individual. If the subject answers more than one question incorrectly he will be disqualified.

** With regards to the planned additional follow-up, the same procedure will be followed.

3 * Who will recruit participants (or acquire charts/records/samples) for this study? (Check all that apply)
Study Staff

3.1 If you are using a third party, specify Third Party Recruiters:

4 Upload any recruitment tools such as screening/telephone scripts and introductory letters (do not upload advertisements here):

Name	Created	Modified Date
------	---------	---------------

There are no items to display

ID: VIEW4E0BCAA0A6C00
Name: v2_Recruitment

View: v2_Advertising

Advertising

1 * Will you be using advertisements to recruit potential participants?

Yes No

ID: VIEW4E0BCCF811000
Name: v2_Advertising

View: v2_Research Related Risks

Research Related Risks

If you uploaded a separate research protocol document in the 'Research Protocol' page, cite the applicable section and page numbers from that document in the answer box below.

1 * Individually list each research-related risk, using a separate line for each. Next to each risk, delineate the likelihood/seriousness of the risk, and the provisions for minimizing the risk:

Original ACCOF protocol:

Risks to subjects

Human subjects' involvement and characteristics. This study will involve 142 adult patients with asymptomatic carotid artery stenosis, and 142 adult subjects without carotid stenosis but with one or more vascular risk factors (hypertension, diabetes, prior cardiovascular disease, or smoking). No patients with a prior stroke, pregnant women, prisoners or children will be included. The vulnerability of the study population will be limited to the fact that they are patients with a risk for stroke.

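### The stroke-correlate analysis expects 5 to 10 strokes where 142 patients over 2 years give about 3 to 6, and what it concludes is reported only if the result warrants it

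*Combined protocol and SAP*

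**What the plan says.** Sample Size and Data Analysis, item 2, contains three relevant statements under its potential difficulties and additional analyses.

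- The additional Aim 1 analysis of post-recruitment stroke cites prior randomized trials and expects that "approximately 1-2% of our patients per year will suffer a stroke".
- The additional Aim 2 analysis on stroke plans to use plaque, microembolic, inflammatory marker and perfusion information recorded before each stroke. It concedes that stroke is not the study's focus and that "these 5 to 10 patients will be too few to derive statistically strong conclusions".
- It then says that the available data will be analysed, and that the investigators will "report additional conclusions on plaque correlates of stroke, if the information is hypothesis-generating".

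The group sizes and follow-up stand elsewhere.

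- Research Related Risks, item 1: "This study will involve 142 adult patients with asymptomatic carotid artery stenosis", alongside 142 controls without stenosis.
- Justification, Objective, & Research Design, item 1: "The study will recruit 284 subjects".
- Study Procedures, item 3: "Duration of participation for subjects will be for 2 years following enrollment". A further paragraph there says that "participation will extend for another two visits after their 2 year follow-ups have been completed for already enrolled patients".
- Study Procedures, item 1: stenosis patients have plaque imaging, embolic counts, markers and perfusion at baseline, 1 and 2 years. Controls have one ultrasound to exclude stenosis, plus cognitive testing.

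**The concern.** The expected count does not follow from the plan's own rate, group size and base follow-up. The stated 5 to 10 is close to double what those inputs give. It is near what one gets by counting the controls, who cannot contribute to an analysis of plaque correlates.

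The reporting clause is the more consequential half and does not depend on the count. Analysis of the data is unconditional, but conclusions are tied to whether the information proves hypothesis-generating. No criterion, comparison group or method is given, so the result itself decides what is reported. With a handful of events and many candidate features, a difference that stands out by chance could be reported while the unremarkable features go unmentioned. Once the data have been seen, this cannot be repaired.

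**Working it through.** **Inputs**

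- Annual stroke rate r: 1% to 2% (additional Aim 1 analysis on stroke). The same paragraph speaks of removing the stenosis after a stroke, so the rate describes stenosis patients.
- Stenosis patients: 142 (Research Related Risks, item 1). All subjects: 284.
- Follow-up T: 2 years per participant (Study Procedures, item 3).

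**Formula.** Expected strokes = n × T × r, checked against the compounded form n × (1 − (1 − r)^T).

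**Can 5 to 10 be reproduced?** The documents do not show how it was obtained. Candidate routes:

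| n | T (years) | at 1% | at 2% |
|---|---|---|---|
| 142 | 2 | 2.84 | 5.68 |
| 142 | 3 | 4.26 | 8.52 |
| 142 | 3.5 | 4.97 | 9.94 |
| 142 | 4 | 5.68 | 11.36 |
| 284 | 2 | 5.68 | 11.36 |

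The row for 142 patients and 2 years is the base plan. Compounding changes it only to 2.83 and 5.62. Neither end matches 5 or 10.

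Solving for the follow-up that 142 patients would need:

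- 5 / (142 × 0.01) = 3.52 years
- 10 / (142 × 0.02) = 3.52 years

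Solving instead for the annual rate over 2 years:

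- 5 / (142 × 2) = 1.8%
- 10 / (142 × 2) = 3.5%

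**How likely are the stated counts on the base plan?** Take strokes as binomial with n = 142 and 2-year risk p = 1 − (1 − r)², which is 0.0199 at 1% and 0.0396 at 2%.

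| | r = 1% | r = 2% |
|---|---|---|
| P(at least 5) | 0.15 | 0.67 |
| P(at least 10) | 0.0006 | 0.057 |

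**Which denominator is usable?** The analysis is defined by pre-stroke plaque, embolic, marker and perfusion data. Study Procedures, item 1, gives controls none of these series. The 284 route therefore fits the number but not the analysis.

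**Direction of what is left out.** Justification, Objective, & Research Design, item 2, has patients exit at stroke, TIA or revascularization, and drops those whose first 3D imaging shows less than 40% narrowing. Full 2-year exposure for all 142 is therefore slightly generous, and 2.8 to 5.7 leans high for the base plan.

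**The case against.** The strongest objection concerns follow-up. Study Procedures, item 3, extends participation by two visits for patients already enrolled. Item 4 has late entrants followed to the end of a project of about 4 years. If entry were even over 24 months and everyone were followed to month 48 (an assumption), mean follow-up would be (24 + 48) / 2 = 36 months, giving 4.3 to 8.5 strokes; at 3.5 years it would be 5.0 to 9.9. The extension names only the cognitive battery and a genetic blood sample, but that does not rule out later strokes, because the earlier visits supply the pre-stroke data. This stands in part. A reader might infer that 5 to 10 can arise only from counting controls or from following everyone for 4 years; the table shows that this is not so. What remains is that the stroke paragraph states neither denominator nor follow-up, and that the base plan does not give its figure.

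A second objection is that hypothesis-generating may simply describe the evidential status of any conclusion, in a paragraph already frank about its limits. That is fair as to tone, and the text does not establish an intention to publish selectively. But the clause is still worded as a condition, and nothing says what satisfies it.

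A reader might also count the 14 features listed for Aim 2 in Justification, Objective, & Research Design, item 2, and infer a 51% chance of a false finding (1 − 0.95^14 = 0.51). The documents do not support this as a magnitude. The stroke analysis specifies no test, no 5% threshold and no set of comparisons, and the features are not independent: the composition percentages are shares of one plaque, and the areas and volume measure the same plaque.

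Finally, little depends on the count. No power calculation, stopping rule or hypothesis test shown in the documents uses 5 to 10. The plan says that stroke attrition is allowed for in the power analysis, but a lower count would only reduce that attrition. This stands and limits the severity.

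**Conclusion.** The point holds as a minor one. On 142 stenosis patients, 2 years and 1-2% per year, the expectation is about 3 to 6 strokes, not 5 to 10. It rests on the base follow-up; a mean of about 3.5 years would bring the stated figure back, but the plan does not claim that. The lower count strengthens the plan's own caution rather than weakening any conclusion.

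The conditional reporting clause is a separate weakness whichever count is right. It calls for unconditional descriptive reporting. It does not justify forbidding every test or comment on correlates of stroke: the analysis is openly exploratory, and a ban would go further than the problem requires.

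**What to change.** Make two changes in the additional Aim 2 analysis on stroke.

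1. Restate the expected number as about 3 to 6 strokes and give its basis (142 stenosis patients, 2 years, 1-2% per year). Alternatively, state the longer mean follow-up that yields 5 to 10, about 3.5 years.
2. Replace the conditional clause with wording such as: *All strokes will be listed with their pre-stroke plaque, embolic, marker and perfusion values, whatever they show. The results will be reported descriptively and labelled exploratory.*

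The cost is a few sentences and a slightly less favourable expected count. Data collection, sample size and the main analyses do not change.
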